- 1. *Communication Strategies* Pharmacists and pharmacy staff in intervention communities will use various public communication strategies, including:
 - a. targeted mail outs and/or phone calls by pharmacies to individuals in their databases based on risk factors for contracting and/or transmitting vaccine-preventable disease (e.g., immunosuppressant medications, recent birth in family)
 - b. timed marketing linked to other vaccine clinics (e.g., influenza clinics) and awareness campaigns (e.g., back-to-school advertising)
- 2. *Payment mechanisms* Intervention communities will provide vaccine through the following payment mechanisms, based on the study vaccine:
 - a. universal vaccination with "publicly funded" vaccine (vaccine provided to individual without charge (i.e. Tdap vaccine))
 - vaccination using a co-pay model (individuals receive vaccine at no cost after paying a designated co-pay fee comprised of the pharmacy dispensing fee and any administration fee charged by the pharmacist immunizers (i.e. high-dose TIV); and
 - c. vaccination using the current private market model where vaccine would be purchased either by the recipient or through insurance (standard of care control arm, (i.e. Meningococcal serogroup B, Meningococcal serogroup ACWY and highdose TIV influenza, herpes zoster, and travel health vaccines).

The non-intervention control arm will be the current model wherein a patient specifically requests a vaccination or the pharmacist offers this option while the patient is in the pharmacy. This non-intervention arm will be compared to the intervention arm.

Inclusion criteria

Inclusion criteria for the selection of the four communities include population size (approximately 30,000 adults >18 years of age), stable population, service by a centralized regional hospital and local community hospitals, availability of community pharmacies, interest and availability of community pharmacists (sufficient numbers of pharmacists qualified to provide vaccinations), and lack of substantial health care spill over to adjacent communities. Spill over is defined as a pattern of health-care utilization where patients regularly receive care at different regional health centres. Communities will be geographically separated to minimize potential spill over.

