5 ETHICAL AND REGULATORY CONSIDERATIONS

5.1 Informed Consent Process and Documentation

This study will be conducted in accordance with all Research Ethics Board requirements. The protocol and all related materials will be submitted to the local independent Research Ethics Boards of the Canadian Center for Vaccinology, Halifax (Nova Scotia Health Authority provincial Research Ethics Board, and Horizon Health REB in New Brunswick), and the Child and Family Research Institute (CRFI), Vancouver (they will be responsible for data management for the AEFI survey only) for review and approval. If the survey is administered in other provinces, it will be submitted to the appropriate REBs. All REBs are constituted in conformance with the Canadian Food and Drug Act and Regulations (C05.005, C05.006). A copy of the REBs' letters of approval for the study will be kept.

No changes will be made to the protocol without REB approval. Pharmacists/pharmacies will be able to withdraw their participation from the study at any time without giving a reason.

Participating Pharmacies

For the pharmacy intervention, the participants are the pharmacies that agree to carry out the study intervention rather than members of the public. Pharmacies will be able to withdraw from the study at any time.

General Public and Healthcare Providers' KABB

Survey participants will receive an information sheet providing them with information about the survey prior to completing the online survey. A consent statement will be included as the first question of the survey. An affirmative answer will be required to proceed with the survey. The participants will be notified that they can withdraw from the study at any time until the survey is submitted. Completion of the online survey implies consent. Surveys are anonymous and participants will not be able to withdraw once they have submitted their questionnaire as the survey instrument cannot be traced back to the original participant.

Adverse event following immunization survey

An information sheet will be provided to influenza vaccine recipients and participants will be required to indicate their consent on the introductory page of the online survey in order to proceed to the survey.

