
2. AEFI Surveys. Point estimates and exact binomial 95% confidence intervals will be calculated for the proportion of influenza vaccine recipients who register for the AEFI survey and the proportion who complete the survey. Descriptive statistics will be used to compare proportions registering and completing the survey among intervention versus control communities. Overall frequency of severe adverse events and the frequency of specific health events (e.g., injection site pain that prevents daily activities) will be calculated. The frequency of severe AEFI will be compared by influenza vaccine type [e.g., QIV, TIV] and by season (i.e., 2016-17 and 2017-18). The frequency of health events after vaccination will be compared to the background event rate estimated by the control survey.

3. Vaccine coverage. Pharmacy databases will be used to determine the number of doses administered to individuals eligible for receipt of vaccine relative to the total number of clients in the pharmacy database in the eligible age range. A second estimate of coverage will be

ROMEO File #: 1021559

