determined by physician billing data and public health provision of vaccine to physicians relative to the Statistics Canada population age specific census data for that community. A study-specific system of reciprocal notification forms for family doctors will be implemented that is similar to that used for publicly funded routine vaccines. A third estimate of vaccine coverage will be vaccine doses distributed in the participating communities (obtained from the manufacturer) relative to the eligible population based on Statistics Canada census data (2011 and 2016 when available). The fourth estimate of vaccine coverage will be derived from the pre- and postprogram public survey. Binomial point estimates and confidence intervals will be made for vaccine coverage rate within site, and coverage will be compared between and among sites using confidence intervals for the difference of binomial proportions, Fisher's exact tests, and logistic regression. Using a margin of superiority of 10%, when comparing two coverage proportions within site or between sites, a sample size of 298 per group gives 80% power to conclude in favor of superiority when the true difference in proportions is at least 20%, and a sample size of 1209 per group provides 80% power when the true difference in proportions is at least 15%, assuming independent responses. However, it is anticipated that there will be dependence within the family unit regarding the decision to be vaccinated, in which case the precision on the binomial point estimate, and thereby, the required sample size, depends on the size of the family unit and the intraclass correlation. Assuming the family unit to consist of two adults, and under the worst-case scenario in which the decision on vaccination is fully concordant for the two family members, the required sample size per group to detect a specified difference is doubled, to 596 (2418) when the true difference is at least 20% (15%). Estimates of the intraclass correlation will be calculated using data from pharmacy databases and from the public survey portion of the study, and these will be used to adjust confidence intervals and test statistics to accommodate within family dependence (Donner, Brikett, & Buck, 1981).

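### If the change in coverage differs between pharmacies, the family-only adjustment in section 6.2 makes the pharmacy-database intervals too narrow, and the stated 80% power may not hold

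*Combined protocol and SAP*

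**What the plan says.** Section 6.2, item 3, describes the first of four coverage estimates: "Pharmacy databases will be used to determine the number of doses administered to individuals eligible for receipt of vaccine", divided by the number of clients of eligible age on file. Against a 10-point superiority margin, "when comparing two coverage proportions within site or between sites, a sample size of 298 per group gives 80% power" if the true difference is 20 points; for the smaller effect, "a sample size of 1209 per group provides 80% power when the true difference in proportions is at least 15%, assuming independent responses".

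The plan then says that "it is anticipated that there will be dependence within the family unit regarding the decision to be vaccinated". It takes two adults who always decide alike as the worst case and doubles the sizes to 596 and 2418. ICC estimates will be used to adjust intervals and tests for dependence within families. The methods are binomial intervals, Fisher's exact tests and logistic regression. The item gives no pharmacy term, no pharmacy-level ICC and no number of pharmacies.

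Section 5.1 states that for the intervention "the participants are the pharmacies that agree to carry out the study intervention rather than members of the public", and lets pharmacies withdraw at any time. Section 3.1 lists "targeted mail outs and/or phone calls by pharmacies to individuals in their databases" among the communication strategies. The primary hypothesis (section 2.3) is a rise of at least 10% from the level before the intervention.

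**The concern.** Clients of one pharmacy share how fully that pharmacy carried out its part of the bundle. Section 3.1 leaves room for this to vary: contact may be by mail, by phone or both, and some contacts and campaigns are worded as optional. Withdrawal can also change the set of pharmacies between periods.

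In a before-after comparison within a site, a pharmacy whose coverage is always high or always low contributes the same amount to both periods and drops out. A pharmacy whose coverage rises more, or less, than its neighbours' does not drop out. The planned methods, adjusted for family only, treat clients of different families in one pharmacy as independent, so they miss this pharmacy-by-period variation.

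Family-adjusted error shrinks as clients are added; variation over a limited number of pharmacies does not. The larger the client files, the further the interval falls short, and the 10-point claim could then rest on strong effort in a few pharmacies.

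**Working it through.** **Inputs from section 6.2:** margin 10 points; true difference 20 or 15 points; 298 and 1209 per group; family factor 2, giving 596 and 2418.

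**Inputs assumed, because the documents give none:** *k* = 10 pharmacies per site; pharmacy ICC *ρ* = 0.01, 0.02 or 0.05; share of pharmacy variance persisting from before to after *r* = 0.5 or 0.8; 5000 clients per period for a whole-file analysis.

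**1. Reproduce the printed sizes.** No significance level is stated for this test. With one-sided 5%, proportions centred on 50% and V = p₁q₁ + p₂q₂:

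n = (1.645 + 0.842)² × V / (difference − 0.10)²

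- 40% to 60%: 6.183 × 0.48 / 0.10² = 296.8, so 297 (printed 298; power at 298 is 80.1%).
- 42.5% to 57.5%: 6.183 × 0.48875 / 0.05² = 1208.7, so 1209 (as printed; power 80.0%).

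One-sided 2.5% gives 377 and 1535, which do not match. Full concordance in pairs gives a design effect of 1 + (2 − 1) × 1 = 2, hence 596 and 2418.

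**2. Add pharmacy-by-period variation.**

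Var(difference) = 2V/n + Vρ(1 − r)/k; power = Φ[(difference − 0.10)/SE − 1.645]

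This is the power of a test that uses the correct standard error. If all pharmacies change alike (r = 1), the second term is zero and power stays at 80%. Example, n = 596, ρ = 0.02, r = 0.5: 0.001611 + 0.000480 = 0.002091; SE = 0.0457; 0.10/0.0457 − 1.645 = 0.542; power 70.6%.

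| Case (k = 10) | Power, r = 0.5, ρ = 0.01 / 0.02 / 0.05 | Power, r = 0.8 |
|---|---|---|
| 40% to 60%, n = 596 | 75.2 / 70.6 / 59.5% | 78.1 / 76.1 / 70.6% |
| 42.5% to 57.5%, n = 2418 | 62.5 / 51.1 / 34.3% | 72.1 / 65.4 / 51.1% |
| 10% to 30%, n = 596 | 90.2 / 86.9 / 77.1% | 92.2 / 90.9 / 86.9% |
| 10% to 25%, n = 2418 | 83.2 / 71.8 / 50.0% | 90.6 / 85.6 / 71.8% |
| 40% to 60%, n = 5000 | 99.9 / 98.7 / 85.0% | at least 98.7% |
| 42.5% to 57.5%, n = 5000 | 77.0 / 60.5 / 37.6% | 89.9 / 81.2 / 60.5% |

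With 5 to 20 pharmacies and r = 0.5, the first row ranges from 47% to 78% and the second from 24% to 70%.

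**3. Error of the family-adjusted rule at a true 10-point rise.** V cancels:

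error = 1 − Φ(1.645/R), with R² = [2/n + ρ(1 − r)/k] / (2/n)

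Example, n = 5000, ρ = 0.02, r = 0.5: R² = (0.0004 + 0.0010)/0.0004 = 3.5; R = 1.871; error = 1 − Φ(0.879) = 19.0%.

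| n = 5000, k = 10 | ρ = 0.01 | ρ = 0.02 | ρ = 0.05 |
|---|---|---|---|
| r = 0.5 | 13.6% | 19.0% | 27.1% |
| r = 0.8 | 9.0% | 12.2% | 19.0% |

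**4. What these inputs mean.** The SD of change between pharmacies is √[Vρ(1 − r)]. With V = 0.48 it is about 5 to 11 points at r = 0.5 and 3 to 7 points at r = 0.8.

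**The case against.** A reader might infer that 596 and 2418 cannot deliver 80% power. The documents do not support that. Only variation in change matters, and nothing in them measures it. The between-community SDs quoted in section 1.6 come from another trial at another level and say nothing about change within pharmacies.

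Several features also favour the plan:

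- **Baseline.** Centring on 50% gives the largest variance. Section 1.2 puts adult Tdap coverage well under 10%, and at low baselines the 20-point power mostly survives. Baselines for the other vaccines are not given.
- **Whole files.** The database estimate uses all eligible-age clients, probably thousands. At 5000 per period the 20-point power is at least 85% with 10 pharmacies; the 15-point power can still fall short.
- **Family factor.** Full concordance is pessimistic. With a family ICC of 0.5 (1.5 in place of 2 in step 2) and r = 0.5, power is 84/79/65% at 596, but only 69/55/36% at 2418.
- **Repeat clients.** Many clients probably appear in both periods, and treating them as independent tends to widen the interval.

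A reader might also infer that the whole bundle is run pharmacy by pharmacy. Section 3.1 ties only mail-outs and calls to each pharmacy's own database; payment mechanisms apply across the intervention communities.

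Finally, if the target were only the change in these communities with these pharmacies, pharmacies could be fixed strata. That does not remove the point: section 2.1 aims at the effectiveness of a delivery strategy, and such a claim should not treat clients of one pharmacy as independent.

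**Conclusion.** The gap is real: section 6.2 allows for one level of dependence and omits the level at which the intervention is partly delivered and the database estimate is collected. Its consequence is conditional on the change differing between pharmacies, which the plan's wording makes plausible but does not quantify.

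The interval concern is the firmer half. Under the assumptions above, a nominal 5% error becomes 9% to 27% with whole files. The power concern is weaker for a 20-point effect and stronger for a 15-point effect. A factor of 2 is in any case a worst case for families only, not for the comparison. The point covers the pharmacy-database estimate within a site; the survey and census-based estimates are not samples of pharmacy clients.

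**What to change.** In section 6.2, item 3:

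- Analyse the within-site change from the pharmacy databases with pharmacy as the cluster: either a client-weighted mean of pharmacy-level changes with a t-based interval over pharmacies, or the planned logistic regression with pharmacy and pharmacy-by-period random effects. Keep the family adjustment.
- State that 298/596 and 1209/2418 give 80% power only if the change does not vary between pharmacies, and stop describing the factor of 2 as the worst case.
- Give the actual number of pharmacies, and the power for it over a range of pharmacy ICCs and baselines.

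The cost is plan wording and some programming. Pharmacy identity should already be known, since data come from each pharmacy's own database, so no new participants or data are needed. The downside is wider intervals and a less favourable stated power.

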7 STUDY HOLDING RULES AND SAFETY MONITORING

As the study involves vaccines that are authorized for use in Canada a Data Monitoring and Safety Committee will not be constituted and no formal study holding rules will be established. Safety monitoring is described under the description of AEFI surveys and reporting.

Confidentiality of Data and Access to Participant Records

Survey data will be confidential. All records for the KABB survey will be maintained in a safe and secure location at CCfV and/or on a secure server that will be only accessible to trained study staff. The AEFI survey data will be stored on a secure server hosted and supported by the Child and Family Research Institute (CFRI) in Vancouver. The database will be accessible through a secure web application with personal passwords for research staff. Participant contact information (email address, first name, telephone number) will be stored in REDCap. Only research team members at CCfV will have access to participants' contact information (names, email addresses, phone number).

Auditing

Audits or inspections may be made by the Research Ethics Board to ensure that the study has been conducted in accordance with the protocol, as applicable.

ROMEO File #: 1021559

Stipends for Participation

Participants who complete the KABB Surveys (General Public Survey and Health Care Providers Survey) will be offered the opportunity to be entered in a draw for a chance to win a \$100 gift card to a restaurant of their choice. Participation in the draw is completely optional. If they choose to participate in the draw, they will be asked to provide their email address; however, they are informed that their email address will be stored in a separate dataset, which will **not** be linked to their survey responses. No compensation will be provided to the pharmacists who are involved in the Vaccine Coverage Demonstration Program as well as participants who complete the Adverse Events Following Immunization (AEFI) Survey.

Adverse Event Compensation and Insurance

Not applicable.

8 ADMINISTRATIVE MATTERS

8.1 Publication Policy

Study result manuscripts will be initiated and led by the Lead Investigators and reviewed by all other coinvestigators who form part of the coverage, KABB and AEFI working groups and submitted to peerreviewed journals and scientific meetings. All publications and presentations will be subject to the publication policies of the Canadian Immunization Research Network (CIRN).

8.2 Knowledge Translation Plan

As a community-intervention project, the public and immunization providers will be involved in the project during its implementation. Different communication strategies will be tested in this project, and a change in KABB is an outcome measure of the study. Post-program KT will include presentations to stakeholders in the participant communities, engagement of knowledge users and decision makers through feedback sessions, presentations, meetings, and publications. CIRN's Stakeholders Advisory Committee and CIRN's contacts with provincial/territorial and national advisory committees will also be employed.

8.3 Data Management

Data management will be the responsibility of the Data Center at the Canadian Center for Vaccinology. Data management and analysis will be performed on the secure server at CCfV. For the KABB survey, data will be stored in SAS version 9.4 or higher on an Intel Xeon E5-1650 v2 1U rackmount server running the CentOS Linux operating system. Daily differential tape backups are performed in addition to weekly full tape backups.

The cleaned data will then be transferred to the final analysis dataset in the project account. A computer program to perform edit checks will then be run to pick up any data inconsistencies and any invalid values.

The AEFI surveys will be administered using REDCap software on a secure server hosted and supported by the CFRI in Vancouver, the same platform used by CANVAS influenza vaccine surveillance. The database will be accessible through a secure web application with personal passwords for research staff, providing a secure environment (encryption, firewalls, frequent backups and recovery plan). Survey data (without contact information) will be downloaded to the CCfV server for analysis. Integrity of the KABB and AEFI datasets will be assured by limiting access through passwords and account control. The Computer Centre Manager, upon direction from the Data Manager provides access to computer accounts. Once the dataset has been moved to the project account it is accessible only by the Data Manager or designate. Before the final analysis is run, the datasets will be locked to updates.

8.4 Record retention

Following closure of the study, the investigator will maintain all site study records in a safe and secure location for seven years. The records will be easily accessible, when needed (e.g., audit or inspection). The investigator/institution will notify the REB of any changes in the archival arrangements, including, but not limited to, archiving at an off-site facility or transfer of ownership of the records in the event the investigator leaves the site.

8.5 Quality assurance

REB audits/inspections can occur at any time during or after completion of the study. If an audit or inspection occurs, the investigator and institution agree to allow the auditor/inspector direct access to all relevant documents and to allocate their time and the time of their staff to the auditor/inspector to discuss findings and any relevant issues.

8.6 Provision of study results to investigators

Where required by applicable regulatory requirements, an investigator signatory will be identified for the approval of the study report. The investigator is encouraged to share the summary results with the study participants, as appropriate.

8.7 Timeline

The project is planned for three years and will consist of a pre-program phase, a program phase, and an analysis phase.

Pre-program phase: 6 months

- Administration of pre-program provincial health care provider surveys
- Administration of pre-program community public surveys
- Roll out of program information and training of practitioners

Program phase: 2 years

- Roll out of program to public
- Program delivery
- Ongoing surveillance activities for coverage rates and AEFI

Post program phase: 1 year

ROMEO File #: 1021559

- Administration of follow up community public survey
- Administration of follow up community health care provider survey
- Outcome analyses, publication and knowledge translation activities

REFERENCES

- Azjen, I. & Timko, C. (1986). Correspondence between health attitudes and behaviour. *Journal of Basic* and Applied Pyschology, 7(4), 259-276.
- Briss, P. A., Rodewald, L.E., Hinman, A.R., Shefer, R.A, Bernier, R.R. et. al. (200). Reviews of evidence regarding interventions to improve vaccination coverage in children, adolescents and adults. *American Journal of Preventive Medicine, 18*(Supplement 1), 97-140.
- Canadian Pharmacists Association (January 4, 2012). Pharmacists once again ranked the most trusted profession in Canada. Retrieved from: http://www.healthactionlobby.ca/fr/media-centre/members-in-the-news/93-pharmacists-once-again-ranked-the-most-trusted-profession-in-canada.html (Accessed April 6, 2014)
- Canadian Pharmacists Association (2015). Pharmacists' expanded scope of practice. Retrieved from: http://www.pharmacists.ca/index.cfm/pharmacy-in-canada/scope-of-practice- canada/.(Accessed February 13, 2015)
- Colgrove, J. (2007). Immunity for the people: The challenge of achieving high vaccine coverage in American history. *Public Health Rep., 122*(2), 248-257.
- Corace, K. M., Srigley, Jocelyn A., Hargadon, Daniel P.,Yu, Dorothy, MacDonald, Tara K., Fabrigar, Leandre R. & Garber, Gary E. (2016). Using behavior change frameworks to improve healthcare worker influenza vaccination rates: A systematic review. *Vaccine*, *34*(28), 1-8.
